 Yes	 X No (If Yes, please contact PRO for a separate review)
------------------------------	-------------------------------------------------------------------------------------------------------------

9. Additional Reviews

a) Has the research project received a scholarly, scientific, or peer review prior to this submission (this may involve a review by a funder, faculty supervisor, or a departmental committee):

 Yes, specify: [name], [name]
 No (NB: IRB recommends a prior scholarly review for studies that are more than minimal risk)
 Pending, specify:

b) Will this research require review by any of the following (check all that apply):

None – UCR IRB is the only approval required

Other (e.g., UCR or non-UCR entities – such as UC [Reliance](#) Registry, [SMART IRB](#) or another IRB)

Specify entity and status of review:

UCR Institutional Biosafety Committee ([IBC](#)): Research using biohazardous materials including any human-derived materials such as blood, body secretions, and tissues, primary and established cell lines

UCR Stem Cell Oversight Committee ([SCRO](#)): Research using human pluripotent cells

UCR Institutional Animal Care and Use Committee ([IACUC](#)): Research using vertebrae animals

II – Study Summary

10. Abstract (suitable for a lay audience)

(Max ¼ page)

In this study we will evaluate the impact of a pre-operative instructional video for patients undergoing a minimally invasive gynecologic surgery. The video will educate patients to understand what to expect and how to take care of themselves after the procedure. The effectiveness of the video will be evaluated via a questionnaire to see if patient's who watched the video had better recovery outcomes, greater understanding, and less anxiety when compared to the group of patients who did not watch the pre-operative video.

11. What is the scholarly rationale for this study?

(Max ½ page)

Minimally invasive gynecologic procedures are considered lower risk than highly invasive surgeries, however, any surgical procedure can be a source of anxiety and fear for patients (1). Studies show that pre-operative videos for various procedures can reduce patient anxiety and increase patient satisfaction (2). Pre-operative video education was shown to increase understanding of their operation and lessen feelings of uncertainty in patients who received a lumbar puncture. Another study found that interaction between the patient and physician in addition to a video was more effective than an interview alone or interview with written material when measuring patient satisfaction and the amount of information gained (3). This is important because pre-operative anxiety and confusion can lead to poorer outcomes and recovery post- surgery. We want to add to this collection of data and see if the same results appear when pre-operative audio-visual material is shown to patients before they undergo their scheduled minimally invasive gynecologic surgery.

12. What are the study hypotheses or research questions?

(Max ¼ page)

1. Will the patients who watch the pre-operative will show decreased anxiety and uncertainty about their procedure when compared to the control group?
2. Will increased understanding of the information shared in the video result in less pain medication usage, less ambiguity and thus increased compliance with post-operative care instructions, and quicker recovery?

III – Study Design and Methodology

13. Study Timelines

Estimated start date for involvement of participants: Upon IRB Approval

Estimated completion date for the involvement of participants: 6 –9 months.

14. Location of Research

a) Where will this study take place? If it's a collaborative study, provide details regarding other site(s). If there is an online component, provide details.

(Max ¼ page)

UCR Women's Health Clinic. Letter of access from [name] attached

b) If research is taking place within a community or an organization, describe how access will be obtained.

Are there any special considerations for obtaining consent? Access letters may be requested from the community or organization. Sample Access Letter template can be found on the [ORI Resources page](#). Attach any relevant supporting documentation as appendices.

(Max ¼ page)

N/A

15. Participant Population: Please describe the participants/subjects. List the inclusion/exclusion criteria.

Include any age, language, gender, or race-related inclusion/exclusion criteria and provide a justification for the use of these criteria. If applicable, please provide a rationale for your choice in sample size and/or sample size calculation.

If you are conducting research in languages other than English, translated versions of the participant-facing research materials (e.g., informed consent, recruitment materials, measures, etc.) must be submitted for review along with the [Certificate of Translation form](#).

(Max ¼ page)

Participants/Sample Size: Female patients who have been recommended for minimally invasive gynecologic surgery. A total of 100 patients will be enrolled in this study at UCR Women's Health Clinic. Statistical power. To rationalize the consideration of statistical power, we determined that 100 subjects will be needed to predict a difference of improvement in patient's post-operative experience ranges 20% or greater.

Inclusion criteria:

- Age 18 – 65 years old
- Surgery with UCR Gynecology physician
- Laparoscopic/robotic surgery
- Same day discharge after surgery
- Can read a survey in English
- Female

Exclusion Criteria:

- Receiving postoperative chemotherapy in the 6-week postoperative period
- Minors under the age of 18

- Postoperative overnight stay
- Laparotomy (open surgery)
- Pregnancy

16. Special Populations

a) Will any participants/subjects be specifically recruited from the following categories listed below (check all that apply):

Under the age of 18

Prisoners, probationers, or parolees

Pregnant women, fetuses, or neonates

Other characteristics that may cause them to be considered 'vulnerable' (e.g., cognitively impaired, educationally/economically disadvantaged, patients, students, staff, history of distrust, etc). Describe:

b) If YES, please justify the use of the above populations, and detailing what additional safeguards will be included in the study to protect the rights and welfare of the subjects and will there be direct benefits. If NO, skip to the next question.

(Max ¼ page)

17. Recruitment: Describe the mode of communication and how participants will be approached. Any recruitment materials, e-mails, & scripts must be submitted for review as appendices.

If you are recruiting participants through a subject pool (e.g., Psychology Department subject pool), please refer to the UCR [Policy on the Use of Subject Pools in Human Subjects Research](#).

(Max ¼ page)

All patients undergoing surgery will be asked to participate in the study. No PHI would be needed for randomization. Patients will be approached in the office setting once they have decided to proceed with surgical management. The surgeon, fellow or clinical research team will approach the participants. Please see the roster for a list of participants involved in the consenting process. They will be handed a "study info" pamphlet that describes the purpose, methods and involvement of the study. The participants will then be scheduled for a preoperative visit. All patients who decide to have surgery are scheduled for a preoperative visit in our office, and patients will be reminded of the study and asked if they want to participate. If consent is granted, the patient will be randomized to receive the preoperative instructions verbally or via an instructional video." The surgeon, fellows and clinical research team are part of the research team.

18. Compensation: Will participants be compensated for their time? Describe the methods, amount and schedule for payment. What will happen to compensation if participants chose to withdraw? If no compensation is being offered, please justify why.

(Max ¼ page)

There is no patient compensation. The study involves no cost to subject participation.

19. Reimbursement: Will participants personally incur any expenses as a result of participation (e.g., fuel, missed work)? If no reimbursement is being offered, please justify why.

(Max ¼ page)

Patients will not incur any expenses as a result of participation.

20. Procedures

a) Describe how human participants will be involved in the research. If there is to be an intervention or interaction with the participants, describe what the researcher and participants will do, who will conduct the procedures, where and when the procedures will take place, how frequently, for how long, what equipment will be used, etc.

(Max ½ page)

Patients will be invited to participate in the study by principal investigator or co-investigator or designated study personnel (Appendix Project Roster) when the patient will be undergoing a minimally invasive gynecologic surgery.

Patient will be consenting in the clinic and randomization will take place the same day patient consent is obtained.

The study group of patients will come to the clinic on the day of their surgery and be asked to watch the informational video about what to expect after their procedure and instructions on how to recover. They will be encouraged to ask their provider any follow up questions. [The instructional video is approximately 10 minutes long.](#)

The control group of patients will receive the standard patient education in place before the procedure and will also be able to ask to follow up questions from their provider.

Both groups will be scheduled for their routine two-week postoperative visit. Some patients schedule a telehealth postoperative visit, if a telehealth visit is scheduled, then a text or email will be sent. If the patient comes in person, the option of filling out the questionnaire in paper form, receive text or email to complete the survey. [The survey will take approximately 10 minutes to complete.](#)

Our primary outcomes will be patient level of satisfaction with the education they received prior to surgery and its impact on post-operative care which will be measured by the standardized likert scale (1 to 5 scale where 1 = strongly disagree and 5= strongly agree). The survey will include the following objective and subjective measures: Tylenol tablets used (over two weeks), Ibuprofen tablets used (over two weeks), pain scale (1 to 5 scale where 1 = none and 5= very severe). Additional information will be collected from the patient's medical records (ie. office visit notes, telephone encounters, hospital laboratory results, pain medication refill requests). Patients should continue any medication regimen as instructed by their physician up to the day of surgery. Patients will be treated for complications as they would have been treated otherwise. Study duration period will be approximately six months.

b) If you are using a dataset, please list out the variables you will be accessing. If you are using the Psychology Subject Pool, please list out the pre-screening data you will be collecting on your participants.

(Max ½ page)

[Chart review data: Age, Ethnicity, BMI, Smoking status, Narcotic use before surgery, Pain levels before surgery, Preop hemoglobin, Indication for surgery, Surgical procedure, Diagnosis, Presence of other pain disorders such as Interstitial cystitis, fibromyalgia, Intraoperative complications,](#)

[and Intraoperative blood loss.](#)

REDCAP Database will be used for the following purposes:

- Data collection
- Sending links to view the video and questionnaire to patient(s)

21. Deception

a) Does this study involve deception or intentional lack of disclosure?

Yes X No

b) If YES, justify and indicate how participants will be debriefed. Indicate if participants are free to withdraw or selectively edit data after being fully debriefed. If NO, skip to the next question.

(Max ¼ page)

22. Research Results: If relevant, please describe what information/feedback, if any, will be provided to the subjects and/or communities after their participation in the project is complete. How will they be able to access the information? If relevant, describe the debriefing process.

Individual results will not be shared with subjects.

23. Consent Process - Ensure you are following the [UCR Informed Consent Guide](#). Sample Informed Consent Templates can be found on the [ORI Resources page](#).

a) Describe the process that will be used to obtain informed consent. How will it be recorded? Who will be authorized to conduct the process? Note that it's the quality of the consent that's most important not the format.

(Max ¼ page)

Consenting Process:

Patients will be approached when they are scheduling their surgery. Subject will be encouraged to take as much time as necessary to decide on participation on the study. They will be allowed to take an unsigned consent to review and discuss with family member. Subjects will be informed that no matter what they decide regarding participating, the care received from the physician will not be affected. Subjects will be randomized on the same day patient informed consent is obtained.

b) If you are applying for a waiver of documented consent (e.g., verbal, online, etc.) or a waiver or alteration of the consent process (e.g., not obtaining consent at all), please explain how you are meeting the conditions for the waiver or alteration as outlined in the [UCR informed Consent Guide](#).

(Max ¼ page) N/A

24. Will anyone other than the participants provide consent (e.g., parents, guardians, legally authorized representatives, etc.)? Describe the process by which capacity/competency will be assessed.

(Max ¼ page)

N/A

25. Withdrawal: Where applicable, please describe how participants will be informed of their right to withdraw from the study and outline the procedures that will be followed to allow them to exercise this right. Also, what will happen if data has already collected (e.g. previous data will be kept, all data will be destroyed, etc.)?

(Max ¼ page)

Participants or legal representatives will be informed of their right to withdraw from the study at any time, verbally and via the written informed consent form. If the patient wishes to withdraw from the study, the data collected will be discarded.

Participants may be withdrawn at any time during the study, until its completion, at which point the de-identified data will not be able to be withdrawn because the identifying data will have been destroyed and link between coded and records is deleted, projected end 2024. Also, published coded/de-identified data will not be able to be withdrawn.

Procedures for withdrawal will be as follows: access to the key code by approved personnel on the project roster, removal of that coded data from all files, shredding of written records, deletion of electronic records.

26. Privacy, Confidentiality & Data

a) **Privacy: Where and how will participants be providing information? Are the researchers collecting identifying information (e.g., names, addresses, phone numbers, DOBs, phone numbers, licenses, audio/video recordings, etc.)? If yes, please describe:**

(Max ¼ page)

Patient identifying data will be provided via the informed consent and will include name, date of birth, medical record number, address, phone number, email address, and an alternate contact if the patient or legal representative is unavailable. A study number, for example given by REDCAP will be given to each subject P01, with "P" representing patient with a numerical value thereafter will be transcribed on the consent form and the medical questionnaire. The coded medical questionnaire will be completed for pertinent medical history. The documents with identifying information (consent form, HIPAA), will be placed in a sealed envelope for collection, or saved electronically on a password-protected drive, and stored in the office of the clinical PI

b) **Confidentiality: Describe the procedures used to protect the confidentiality of participants. If not relevant, describe any limitations to protecting the confidentiality of participants whether due to the law or method used (e.g., confidentiality is not appropriate). For storage of electronic identifiable information outside of a secure server environment, UCR requires the use of encryption software.**

(Max ¼ page)

All measures will be taken by the study team to protect the confidentiality of every subject's personal health information. All study subjects will be assigned a patient ID. Research data collected will be deidentified and stored in a secured data server with access code protection to access the database. Only certified and designated staff is allowed to access, enter and retrieve the data. All paper format data are stored in a secured location with locks to prevent Reporting of confidentiality. [The code sheet/file will be stored separately from all other data for an additional layer of confidentiality protection.](#)

c) **Data: Where will the data be stored and for how long? Who will have access to identifying information and for what reason?**

(Max ¼ page)

Patient consent forms and will be stored as described in section 26b. The patient consent form will be discarded in compliance with HIPAA policy and procedure once all data is collected and analyzed, which is projected for end 2024. The coded data will be stored and analyzed by personnel on the project roster. De-identified data will be stored indefinitely by UCR personnel on the project roster. [the consent document and the HIPAA authorization form should be maintained for six years to be in compliance with HIPAA requirements.](#)

27. Possible Risks

a) Please check off all potential risks to participants as individuals or as members of a community or to the researchers that may arise from this research. Please acknowledge risks even if remote or unlikely.

Physical Risks (e.g., bodily contact, administration of substance):	 Yes  No
Psychological/emotional risks (e.g., feeling uncomfortable or upset):	 Yes  No
Legal risks (e.g., arrest or subpoena):	 Yes  No

b) Describe the possible risks and consider the probability and magnitude of possible harms and discomforts. Describe the procedures that will be used to minimize potential risks to participants.

(Max ¼ page)

A remote unlikely risk is that the patient could feel more anxiety towards surgery despite the educational videos effort to calm patients concerns. The patient will be validated in her fears and reiterate that the video is meant to improve a patient's understanding regarding upcoming surgery. The patient will also be reassured that she can chose to be removed from the study at any point.

Ethical concerns may be associated with reviewing medical records of each participating patient but in order to prevent release of information improperly, each participating individual including physicians, nurses, receptionists, and the principal investigator will be certified under HIPPA and will properly exercise HIPPA regulations throughout the duration of this research.

- Only members of the study team will have access to the study data
- All study documents will be maintained in a secure location (i.e., a locked cabinet in the locked study coordinator's office [with limited access]) with only authorized research personnel affiliated with the study having access to it
- All electronic data will be stored on a password protected database with encryption, firewall, etc.

28. Possible Benefits

a) Describe possible direct benefits to participants. If there are no direct benefits, please state so. Please note that compensation is not a benefit.

(Max ¼ page)

Taking part in this study may or may not make benefit the subject's health. All reasonable efforts will be made to ensure the safety of each participant by following good medical practice guidelines. Any unanticipated risks will be addressed on a case-by-case basis.

b) Describe possible benefits to communities, society, or scientific knowledge in general.

(Max ¼ page)

The information from this study might help to develop better post operative experience after receiving concise information via video for future patients undergoing similar surgeries.

29. The US research regulations define '*Minimal Risk*' as the probability and magnitude of physical or psychological harm that is normally encountered in the daily lives, or in the routine medical, dental, or psychological examination of healthy persons. (45 CFR 46 & 21 CFR 50)

a) Do you believe your proposed research activities meet the above definition of '*Minimal Risk*'?

X Yes No

b) If yes, please elaborate by engaging your particular IRB proposal with the definition above.

(Max ¼ page)

Patients will be counseled on any risks associated with watching the pre-operative video.

The only problems that are anticipated are data collection loss to follow up.

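### Research question 1 concerns anxiety and uncertainty about the procedure, but the plan describes no measure of either between the education and surgery

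*Combined protocol and SAP*

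**What the plan says.** Section 12 poses two research questions. The first is: "Will the patients who watch the pre-operative will show decreased anxiety and uncertainty about their procedure when compared to the control group". Section 11 says which anxiety motivates the study: "pre-operative anxiety and confusion can lead to poorer outcomes and recovery". The abstract (section 10) states that "The effectiveness of the video will be evaluated via a questionnaire" and lists among the expected effects "greater understanding, and less anxiety when compared to the group of patients who did not watch the pre-operative video". It names no scale and no time of assessment.

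On the intervention, section 20a states: "The study group of patients will come to the clinic on the day of their surgery and be asked to watch the informational video". The content is described as "what to expect after their procedure and instructions on how to recover". Section 17 says that, after consent, "the patient will be randomized to receive the preoperative instructions verbally or via an instructional video".

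On outcomes, section 20a attaches the survey to the two-week visit after surgery, on paper or by text or email. It names satisfaction with the education and its effect on care after surgery (the primary outcomes, scored 1 to 5), counts of Tylenol and ibuprofen tablets, and a 1 to 5 pain scale. Section 20b lists the chart-review variables. Section 15 gives the size: "A total of 100 patients will be enrolled in this study".

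**The concern.** On its natural reading, a question about anxiety over a procedure needs a measurement before the procedure, once the education has been given. The plan describes none. A patient asked two weeks later already knows how the surgery and the recovery went, and that knowledge can shift what she remembers feeling. A smooth recovery may make earlier worry look smaller, and a complication may make it look larger. The arms would then be compared on a mixture of the education's effect and the experience of surgery.

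At stake is the first of the two research questions and the abstract's claim about anxiety. The primary outcomes in section 20a and the sample-size statement in section 15 do not depend on it. The loss is permanent for each patient: a score before surgery cannot be collected afterwards.

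**Working it through.** **1. Is there a measure before surgery anywhere in the plan?** Each described data source, in turn:

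| Source | Timing | Anxiety or uncertainty named? |
|---|---|---|
| Outcome survey (20a) | Two-week visit after surgery | No; satisfaction, tablets and pain are named |
| Medical-record sources (20a) | Not tied to a point before surgery | No; visit notes, calls, laboratory results, refill requests |
| Chart-review list (20b) | Includes pain and narcotic use before surgery | No |
| REDCap links to video and questionnaire (20b) | No time given for the questionnaire | No |
| Coded medical questionnaire (26a) | Not stated | No; it is for medical history |

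Section 27b names increased anxiety about surgery as a possible harm but describes no measurement of it. The number of described measures of either construct between the education and surgery is 0.

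**2. The plan's own figure.** Section 15 gives 100 patients for a difference of 20% or more in post-operative experience. That is not anxiety, and with no significance level, power, SD or control rate stated it cannot be reproduced. The point here does not depend on it.

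**3. What one correctly timed form would deliver.** Inputs: 100 patients in total (section 15). Assumed: 1:1 allocation, two-sided 5% level, two-sample t-test.

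- 95% confidence interval half-width, 50 per arm: t(0.975, 98) × √(2/50) = 1.984 × 0.200 = 0.397 SD.
- With only 40 completed forms per arm: t(0.975, 78) × √(2/40) = 1.991 × 0.2236 = 0.445 SD.
- Difference detectable with 80% power, 50 per arm: 0.566 SD.
- With an optional baseline form and an assumed baseline correlation of 0.5: 0.397 × √(1 − 0.5²) = 0.344 SD.

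**4. Illustration of relying on a two-week score.** Suppose the score at two weeks reflects the video only through anxiety before surgery, and the two scores correlate r. The effect of 0.566 SD then shrinks to r × 0.566:

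| Assumed r | Effect at two weeks (SD) | Power, 50 per arm |
|---|---|---|
| 0.3 | 0.170 | 13.4% |
| 0.5 | 0.283 | 28.8% |
| 0.7 | 0.396 | 50.1% |
| 0.8 | 0.453 | 61.1% |
| 0.9 | 0.509 | 71.3% |

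No document gives a correlation, so this is a range over assumptions, and the conclusion does not rest on it. It also leaves out any direct effect of the video on anxiety during recovery.

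**The case against.** The best counter-argument has four parts.

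- **The questionnaire has not been seen.** The abstract says that a questionnaire will judge anxiety, and the list in section 20a need not be exhaustive. This stands as far as content goes: one cannot say that anxiety is missing from the form. It does not close the timing gap, because section 20a alone says when the survey is completed, and that is two weeks after surgery. The undated REDCap link in section 20b does not establish an earlier time.
- **The video is about recovery.** Anxiety and uncertainty during recovery are fair targets, and two weeks is a reasonable time to ask about them. This also stands. But question 1 refers to the procedure, and section 11 argues from anxiety before surgery. If recovery is what is meant, the question needs rewording.
- **Anxiety is not a primary outcome.** True, and it limits the seriousness. The primary satisfaction rating also looks back, but its subject is the patient's opinion of the education, which can properly be asked later. A state of mind before surgery is harder to recover from memory.
- **The correlation table rests on invented inputs and one causal path.** Agreed; it is illustrative only.

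The documents do not show whether enrolment has begun. Sections 25 and 26c project an end in 2024. If enrolment is complete, only the rewording is left.

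**Conclusion.** The concern holds. The plan describes no measure of anxiety or uncertainty between the education and surgery, and the only outcome survey with a stated time comes two weeks after surgery. Followed as written, it would yield at best recalled or postoperative anxiety: a weak and bias-prone answer to question 1, though not a worthless one.

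Confidence is high on the missing time point. On whether the unseen questionnaire contains an anxiety item, nothing is concluded. The reading that question 1 means anxiety before surgery rests on its wording and on section 11. This should be fixed, but it does not threaten the primary analysis. The precision figures (±0.40 SD; 80% power at 0.57 SD) assume 50 per arm with complete forms.

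**What to change.** 1. Reconcile sections 17, 20a and 20b on when and how the education is delivered: after consent at the preoperative visit, in clinic on the day of surgery, or by REDCap link. The assessment cannot be timed until this is settled.
2. In both arms, add one short anxiety and uncertainty form in REDCap, completed after the education and before surgery, at the same point relative to surgery in each arm. A brief validated scale is preferable; otherwise use one 1 to 5 item for each construct.
3. Compare the randomized arms on this score and report the difference with its 95% confidence interval.
4. Optionally, give the same form at consent, before randomization, and adjust for it.

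**Cost.** Two items × 100 patients = 200 answers, or 400 with the baseline form. A validated scale, assumed to have 6 items, plus 1 uncertainty item gives 7 × 100 = 700 answers. There is also one amendment, and staff must see that the form is completed before surgery in both arms.

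**If the form is not added.** Restate question 1 and the abstract as concerning recalled or postoperative anxiety and uncertainty, confirm that the two-week questionnaire contains those items, and draw no conclusion about anxiety before surgery. This adds no burden for patients, but it gives up the question that section 11 uses to justify the study.

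### Does enrolling exactly the 100 patients said to be needed leave the trial short once some are lost to follow-up?

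*Combined protocol and SAP*

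**What the plan says.** Section 15 (Participant Population) fixes the size: "A total of 100 patients will be enrolled in this study". The sentence that follows justifies it, stating that "100 subjects will be needed to predict a difference of improvement in patient's post-operative experience ranges 20% or greater". This is the only power statement in the document. It mentions no attrition allowance, evaluable number or replacement of lost patients.

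Two other places bear on how many patients reach the analysis. Section 29b, in its answer on minimal risk, says: "The only problems that are anticipated are data collection loss to follow up". Section 25 (Withdrawal) says: "If the patient wishes to withdraw from the study, the data collected will be discarded". Neither gives a rate.

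The outcome is described in Section 20a: "Our primary outcomes will be patient level of satisfaction with the education they received prior to surgery and its impact on post-operative care", measured on a "standardized likert scale (1 to 5 scale where 1 = strongly disagree and 5= strongly agree"). On timing, the same section says: "Both groups will be scheduled for their routine two-week postoperative visit". The survey can be completed on paper, by text or by email.

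**The concern.** A sample-size calculation normally gives the number needed in the analysis, and enrolment is then set higher to cover expected loss. Here the two numbers are the same, while the plan itself names loss to follow-up as its one anticipated problem and discards the data of anyone who withdraws. Patients are randomised on the day of consent and the outcome comes two weeks after surgery, so there is time for patients to drop out.

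If 100 is the number that must be analysed, any loss leaves the trial below its own target. A null result would then be harder to interpret, because the trial might have missed the difference it was built to find.

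**Working it through.** **Inputs from the document.** Enrolment 100 and need 100 (Section 15); a difference of 20% or more, with no scale or base given (Section 15); a 1 to 5 scale, so a range of 5 − 1 = 4 points (Section 20a); loss expected, no rate (Section 29b).

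**Assumed, because the document gives none.** 1:1 allocation, two-sided alpha 0.05, 80% power, a two-sample comparison of means, equal SDs, and loss of 5% to 20%.

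**Step 1: can the 100 be reproduced?** Not uniquely. For means, n per arm = 2 × (1.960 + 0.842)² × (SD/δ)² = 15.70 × (SD/δ)². The 20% could be 0.6 points (20% of a control mean of 3) or 0.8 points (20% of the 4-point range). Taking several SDs:

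| Reading of 20% | SD (assumed) | n per arm | Total |
|---|---|---|---|
| 0.8 points | 1.4 | 48.1, so 49 | 98 |
| 0.6 points | 1.0 | 43.6, so 44 | 88 |
| 0.6 points | 1.2 | 62.8, so 63 | 126 |
| 0.8 points | 1.0 | 24.5, so 25 | 50 |

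Read as a 20-point difference in proportions, 75% against 95% needs 98 in total, and 70% against 90% needs 124. Some inputs land near 100 with almost nothing spare. Others leave room: a need of 88 within 100 enrolled tolerates 12% loss. Others exceed 100 before anyone is lost. The text does not say which applies.

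**Step 2: what does loss cost if 100 analysed gave exactly 80% power?** By the normal approximation the detectable effect is 2.802 × √(2/50) = 0.560 SD. At 45 per arm, power is Φ(0.560 × √22.5 − 1.960) = Φ(0.70) = 0.76. The noncentral t gives:

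| Analysed | Power at the effect detectable with 100 | Detectable effect at 80% power | 95% CI half-width |
|---|---|---|---|
| 100 | 80% | 0.57 SD | 0.40 SD |
| 95 | 78% | 0.58 SD | 0.41 SD |
| 90 | 76% | 0.60 SD | 0.42 SD |
| 80 | 71% | 0.63 SD | 0.45 SD |

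If ten patients were lost from one arm only (50 against 40), the detectable effect would still be 0.60 SD. Starting from 90% power, loss of 5% to 20% leaves about 89% to 83%.

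**Step 3: is loss what decides whether 100 is enough?** With 0.8 points and SD 1.0, power is 98% at 100 analysed and 94% at 80. With 0.6 points and SD 1.2 it is 70% at 100, before any loss. With 0.6 points, moving the SD from 1.0 to 1.2 takes power at 100 from 84% to 70%; losing 20% of patients at SD 1.0 takes it from 84% to 76%. The unstated SD and the reading of 20% can matter more than attrition.

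**Step 4: what would an allowance look like?** If 100 analysed were truly required, enrolment would be 100/0.90 = 111.1, so 112, at 10% loss, or 100/0.80 = 125 at 20%. Nothing in the document establishes that requirement.

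**The case for a change.** The strongest case for acting is that the plan names one problem and its only sample-size sentence ignores it. Any loss at all leaves fewer than 100 analysed, and withdrawals are removed by rule. "Same day discharge after surgery" is an entry criterion and an overnight stay an exclusion, yet an unplanned stay is known only after randomisation and could reduce the number further. A reader cannot tell what 20% means in points, and stating the inputs would cost one reworded paragraph and no patients.

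Much of this stands as a comment on reporting. The analysed number will fall below 100 if anyone is lost, and the inputs are missing. It does not stand as a case that the trial is undersized. The document states no power that the loss could be shown to breach. Unplanned stays lower the count only if those patients are then dropped, which the plan does not say. A two-week survey tied to a routine visit, with paper and electronic options, may keep loss low. A replacement power sentence written by a reviewer would have to supply the test, power, loss rate and meaning of 20%, none of which is in the plan, and would alter no step of the analysis.

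**Conclusion.** No change to the plan follows. The matching figures of 100 are a gap in reporting, not a demonstrated error in arithmetic. Whether the analysed number falls short of the true need cannot be determined from the document.

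Under an assumed 80% power at two-sided 0.05 with 100 analysed, loss of 5% to 20% costs about 2 to 9 percentage points of power and moves the detectable difference from 0.57 SD to between 0.58 and 0.63 SD. A smaller number by itself costs precision and does not bias the comparison of the two arms. Whether discarding withdrawals' data could bias the comparison is a separate question from the sample size.

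An analyst would fill the gap in the ordinary way, reporting patients randomised and analysed by arm and the difference in points with its 95% confidence interval. That interval shows directly which differences the data exclude, whatever the planned power was. The figures rest on 1:1 allocation, a comparison of means with equal SDs and the loss rates shown, all of them assumptions.
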